7.3 Medication Check (SMS text; Day 10)

An SMS/text will be sent to all patient participants 10 days from the baseline appointment with the following information:

- A request for a reply with capsule count.
- A reminder to return the bottles with remaining capsules at the next visit, which would be the re-evaluation.

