2.3 Potential Risks and Benefits

2.3.1 Potential Risks

Risks related to SRP

SRP is a non-surgical procedure that involves mechanical debridement of the roots of the teeth using dental instruments. This procedure may lead to root sensitivity, which may be transient or long term. It can also lead to gum recession and exposure of part of the root in the oral cavity. A periodontal abscess may form within days after SRP, which may cause pain and may require additional dental procedures for drainage. Patient participants will contact their dental practitioner if any adverse event including post-procedural pain, swelling, trauma, or bleeding has occurred.

Risks related to Amoxicillin and Metronidazole antibiotic intake

Antibiotic intake is associated with gastrointestinal adverse events such as fungal infections in the mouth or elsewhere in the body, nausea, and/or diarrhea. Women taking broad spectrum antibiotics are at increased risk of developing a yeast infection due to a reduction in healthy vaginal bacteria. Use of antibiotics may decrease the efficacy of hormonal contraceptives (birth control); use of a secondary method of birth control should be encouraged. It can also lead to adverse events including allergic / anaphylactic reactions. The possibility of adverse events (allergic reaction) will be mitigated with exclusion criteria that eliminate patients with a history of allergy or adverse effects associated with penicillin, Amoxicillin, or Metronidazole families of antibiotics

Patient participants will also have a thorough review of their medication history to prevent adverse interactions with study medications.

After being administered antibiotics, patient participants will be monitored while in the office until treatment completion and discharge to determine if any adverse reaction has occurred. Patient participants who experience allergic or other adverse reactions due to study medications will be referred for immediate medical care as needed. The event of experiencing any severe adverse events with subsequent antibiotic doses is rare, and if that happens, the patients will call their dental provider. The research team will not routinely follow-up with the participants with a text or phone call. Drug-related adverse reactions will be a

reason for discontinuation of the drug as detailed in section 6. All prescribed treatments (outside of the study) will continue as planned.

Risks related to Placebo intake

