Evaluate treatment - related adverse events. (Safety outcome)	The number and severity of adverse events related to SRP plus AMXM versus SRP plus placebo will be recorded to assess the safety of the intervention.	Outcome: Number of serious adverse events (SAEs) and adverse events (SAEs) and adverse events (AEs) identified by practitioners at each study visit, or at unscheduled encounters related, probably related, or possibly related to study participation, during the study period. Documentation of SAEs and AEs will identify if the event was unexpected/expected and unrelated/related to study participation or the intervention, following relevant OHSP reporting procedures for SAEs and AEs.	Continuously throughout the study.

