6.2 Dosage, Preparation and Administration of Study Product

Study drugs will be formulated as capsules (green capsules for Amoxicillin 500mg and blue capsules for Metronidazole 500mg) and dispensed in two separate identical bottles, one of each drug (Bottle A and Bottle B, respectively) as mentioned above. Placebo capsules for Amoxicillin 500mg will be green, identical to the Amoxicillin 500mg capsules and Placebo capsules for Metronidazole 500mg will be blue, identical to the Metronidazole 500mg capsules, and will be dispensed in two separate bottles, similar to AMXM group to maintain care provider and patient participant masking. Two green capsules of Amoxicillin 500mg and two blue capsules of Metronidazole 500mg (AMXM group) or two green capsules of Placebo and two blue capsules of Placebo (Placebo group) will be given to the patient participants as a loading dose 30-60 minutes prior to initiation of the SRP procedure, because of evidence supporting greater benefit when antibiotics are given in conjunction with SRP (Kaner et al. 2007). A loading dose for the AMXM group will equate to 1g of Amoxicillin and 1g of Metronidazole. After the loading dose, each patient participant will be instructed to take one green capsule and one blue capsule every 8 hours for 10 days, in both AMXM and Placebo groups. Medication

bottles will not include any identifiers related to group allocation in order to maintain masking.

The identical labeling of the bottles between the two groups will ensure proper masking for the patient participants, the study staff, and practitioners administering the products.

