6.5 Assessment of Patient participant Compliance with Study Product Administration

Patient participants will be asked to return the medication vials to the dental office at their next visit (6-week re-evaluation) upon completion of the antibiotic / placebo regimen, at which time the practitioner will perform and record a capsule count and will safely store any unused capsules (see additional instruction in Section 6.4 above). For fidelity monitoring regarding compliance with product administration, patient participants will also receive a text inquiry regarding the number of remaining capsules in each bottle on day 10 and reminded to return the medication vials to the office at the reevaluation (6 week) visit. The text response will be recorded by NCC and in case of a discrepancy between self-reported and practitioner-assessed capsule counts, the practitioner-assessed count will be considered as final data. If the patient participant misses returning their bottle at the re-evaluation visit, then a self-reported capsule count will be used for data entering. The training slides will emphasize the need to schedule the second baseline visit within 10 days of initial medication dispensing to ensure antibiotic coverage. Data may be collected within a 30-day time frame from initial medication dispensing, this will not be a protocol violation. If the second baseline visit occurs beyond 30 days from the time of the antibiotic / placebo administration, then the patient participant will be withdrawn from the study. The number of remaining capsules will be recorded, and all patient participants will be analyzed in the originally randomized group consistent with Intention-To-Treat (ITT) analyses principles.

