APPENDIX A: SCHEDULE OF EVENTS

PAAS Schedule of Events

Procedures	Screening/ Enrollment (day 0)	Baseline/ Visit 1a (day 1)	Opt. Visit 1b (day 2-10)	Medication Check (SMS text) (day 10)	Re-evaluation Visit (6 weeks + 3 weeks)	Final Study Visit (12 months, -2,+3 months)	Unscheduled Visit	Early Withdrawal
Signed Consent Form	Х							
Contact Information	Х							
ASA Classification	Х	(X)						
Periodontal Measurements	Х	(X)			Х	Х		
Assessment of Eligibility Criteria	Х	Х						
Review of Medical/Dental History		Х						
Review of Substance History & concomitant medications		Х						
Randomization		Х						
Study Intervention (Medication/Placebo Admin.)		Х						
SRP Procedure		Х	(X)					
Plaque Sample Collection (optional)		Х			Х			
Assessment of Adverse Events		X	Х	X	X	X	X	X
OHIP-5 Self-report Survey		Х			Х	Х		
Oral Hygiene Instruction (OHI)		Х	(X)		Х	Х		
Capsule count				Х	Х			
Compliance with OSC visits						Х		
Record Withdrawal reason								Х

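### Appendix A schedules adverse-event assessment at the day-10 text message, but the procedures give that message no adverse-event question, so nothing common to all participants is asked between Visit 1 and re-evaluation

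*Protocol*

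**What the plan says.** Treatment-related adverse events are a stated between-arm outcome. Section 3.2 of the protocol says: "The number and severity of adverse events related to SRP plus AMXM versus SRP plus placebo will be recorded". It counts events that practitioners identify at study visits or unscheduled encounters, and its time frame is the whole study.

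On when participants are asked, the protocol speaks in several places:

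- **Appendix A** has a row headed "Assessment of Adverse Events", marked in every column except screening. The marked columns include optional Visit 1B and the day-10 text message.
- **Section 7.3** lists the content of that message: "A request for a reply with capsule count" and "A reminder to return the bottles with remaining capsules at the next visit, which would be the re-evaluation". Nothing else is listed.
- **Section 6.5** presents it as compliance monitoring, a "text inquiry regarding the number of remaining capsules in each bottle on day 10".
- **Section 2.3.1**, discussing drug reactions, says: "The research team will not routinely follow-up with the participants with a text or phone call".
- **Section 7.2** gives Visit 1B two tasks, the remaining scaling and root planing and an instruction to keep taking the capsules. Visit 1, re-evaluation and the final visit each have an explicit step for recording adverse events.
- **Sections 9.1 and 9.2** require staff to ask about adverse events at every study visit. Between visits, participants are expected to contact their practitioner.

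The course itself is short: participants "take one green capsule and one blue capsule every 8 hours for 10 days" after the loading dose (section 6.2).

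**The concern.** Whoever builds the text message will work from section 7.3, and the result will lack an assessment that Appendix A schedules. This is a matter of data collection, so an analysis plan cannot repair it afterwards.

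The timing matters because of the events in question. Sections 2.3.1 and 9.3.2 name nausea, diarrhoea, fungal or yeast infection and allergic reactions as drug risks. Many such events can start and finish well before a visit at 6 to 9 weeks. Grading also needs detail that fades: section 9.3.3 grades by effect on daily activities, and section 9.3.1 judges relatedness partly by timing and by whether the event settles when the drug is stopped.

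At stake is the harm side of the comparison. Section 12.2 powers the trial for a 0.2 mm benefit that it calls small, and the background frames the question as one of antibiotic stewardship. If milder events go unrecorded, the absolute excess on antibiotics looks smaller than it is. Other safeguards cannot recover them: the protocol plans no halting rules and no interim safety review, and the six-monthly report to the Medical Monitor can reflect only what was recorded.

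**Working it through.** **1. The passages side by side**

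| Contact | Appendix A marks adverse events | Procedural text |
|---|---|---|
| Visit 1 | Yes | Section 7.2 has the step |
| Optional Visit 1B | Yes | Section 7.2 omits it; sections 9.1 and 9.2 cover it as a study visit |
| Day-10 text message | Yes | Sections 7.3 and 6.5 omit it; sections 9.1 and 9.2 speak of visits, so do not supply it |
| Re-evaluation | Yes | Section 7.4 has the step |

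The day-10 contact is the only one of the four for which no procedural text delivers what Appendix A schedules. It is also the only scheduled contact common to all participants between Visit 1 and re-evaluation, because Visit 1B is held only when treatment is not finished at Visit 1 (section 4).

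**2. The calendar**

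Inputs: a loading dose of 2 capsules per bottle, then one from each bottle every 8 hours for 10 days (section 6.2); re-evaluation at 6 weeks plus up to 3 weeks (section 7.4).

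- Check on course length: 2 + 3 × 10 = 32 capsules per bottle, which agrees with the fill stated in section 6.1.2.
- Re-evaluation window from treatment: 6 × 7 = day 42 to (6 + 3) × 7 = day 63. This is the plan's own 6 to 9 weeks.
- Gap from the end of the course: 42 − 10 = 32 days to 63 − 10 = 53 days, or about 4.6 to 7.6 weeks.

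An event at the start of the course is therefore asked about roughly 6 to 9 weeks later, and one at its end roughly 4.6 to 7.6 weeks later. With a question at day 10, the first solicitation common to all would come 32 to 53 days sooner.

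**3. What Visit 1B covers**

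Appendix A places it at day 2 to 10. Asking at day 2 covers little of the course, and asking at day 10 covers nearly all of it. The protocol does not give the share of participants expected to have this visit, so the covered fraction cannot be computed.

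**4. Effect on the safety comparison (illustration only)**

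The protocol gives neither event rates nor a capture rate. Assume true rates p1 = 25% on antibiotics and p0 = 10% on placebo, and one capture fraction c in both arms. Then

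observed difference = c × (p1 − p0).

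| c | Observed rates | Observed difference |
|---|---|---|
| 1.00 | 25% vs 10% | 15 points |
| 0.75 | 18.75% vs 7.5% | 11.25 points |
| 0.50 | 12.5% vs 5% | 7.5 points |

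The ratio stays at 25/10 = 2.5 throughout. Only the absolute difference shrinks. Sample size, power and alpha for the primary outcome are untouched.

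**The case against.** A reader might infer that adverse events are not solicited at all during the course, and that the safety outcome rests on recall at 6 to 9 weeks. The documents do not support that.

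- Sections 9.1 and 9.2 require inquiry at every study visit. Visit 1B is a study visit meant to fall within 10 days of Visit 1, and Appendix A marks it too. Its missing line in section 7.2 is a listing gap under a general rule.
- Other routes feed the outcome. Participants are told to contact their practitioner, who records the event. Unscheduled visits are documented (section 7.7) and count under section 3.2. Participants are observed in the office after the loading dose, and early discontinuation of the capsules is noted (section 5.5.2).
- The magnitude is assumed. The halving follows from choosing 50% capture and a single capture fraction for all events.

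All of this stands, and it limits the point to participants without a Visit 1B, to the part of the course after a Visit 1B where one is held, and mainly to mild and moderate events that people do not report unprompted. It does not remove the contradiction over day 10.

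It could also be argued that the Appendix A mark is the error and that a bare capsule count was intended. The document cannot settle that, but the passages would still need to be reconciled.

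**Conclusion.** The contradiction is real. Appendix A schedules adverse-event assessment at the day-10 message; sections 7.3 and 6.5 give the message no such content, and section 2.3.1 points the other way. The consequence is a gap in solicitation common to all participants from Visit 1 to day 42 to 63, ending 32 to 53 days after the course.

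The likely direction is under-recording of milder drug events and a smaller absolute difference between arms. This assumes that unprompted reports and later recall miss some events, and that capture is similar in the two masked arms. The size is unknown, because the protocol gives no event rates, no capture rate and no expected share of participants with a Visit 1B. The reduction from 15 points to between 7.5 and 11.25 is an illustration, not an estimate.

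This should be corrected because the outcome is a stated one and the remedy is cheap. It does not threaten the primary analysis.

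**What to change.** 1. Add one question to the day-10 message: any new symptom since starting the capsules, yes or no, and if yes, which.
2. State the route for a positive reply. Section 6.5 has the national coordinating center recording text replies, while sections 9.1 and 9.2 have the practice completing the adverse-event form with help from the node coordinator. A yes should pass from the coordinating center to the node coordinator and the practice, for entry on the existing form.
3. Add an adverse-event line to the Visit 1B list in section 7.2.
4. Include the day-10 contact in the safety-outcome wording of section 3.2, which now covers only visits and unscheduled encounters.
5. Reconcile sections 2.3.1, 6.5, 7.2 and 7.3 with Appendix A.

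The message already goes to everyone and its replies are already recorded. The cost is coordinator time to monitor replies from about 544 participants and hand over the positives, plus the edits. Sample size and treatment do not change.

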7.4 Intermediate Visits

Re-evaluation (Visit 2, 6 weeks + 3 weeks)

 Record adverse events as reported by patient participant or observed by practitioner.

- Patient participant completes OHIP-5.
- Record patient participant's compliance with medication schedule by capsule
 count in the medication bottles. Practice will collect any returned leftover pills and
 mail them back to the PI's team in a provided pre-paid envelope after the practice
 has completed re-evaluation visits for all patient participants.
- Practitioner collects optional subgingival plaque specimen using paper points.
- Practitioner records periodontal measurements:
 - Probing Depth (PD) (full-mouth)
 - Bleeding on Probing (BoP) (half-mouth diagonal)
 - Gingival Recession (GR) (half-mouth diagonal)

After the re-evaluation visit, the patient participant will continue care for their periodontal disease as is typical for the practitioner. During training, all practitioners will be asked to perform q3-4month maintenance visits as per their practice standards. The number of maintenance visits will be recorded on the Final Visit Checklist eCRF.

7.5 Final Study Visit

Final Study Visit (Visit 3, 12 months -2, + 3 months) (visit range 10-15 months)
Record adverse events as reported by patient participant or observed by practitioner.

- Patient participant completes OHIP-5.
- Practitioner/office staff records patient participant's compliance with standard of care maintenance visits (D4910).
- Practitioner records periodontal measurements:
 - Probing Depth (PD) (full-mouth)
 - Bleeding on Probing (BoP) (half-mouth diagonal)
 - Gingival Recession (GR) (half-mouth diagonal)
- Practitioner/office staff provides final instructions to patient participant (e.g., follow-up on ongoing adverse events)

7.6 Withdrawal Visit

If a patient participant withdraws from the study, the following is completed:

Record date and reason for withdrawal.

- Record information needed to address a safety event that may have led to the patient participant's withdrawal from the study.
- No further information will be recorded after patient participant withdrawal request. Any information collected until that time will be used for the ITT analysis.

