5.5 Patient participant Withdrawal or Discontinuation from Study Procedures/Intervention

5.5.1 Reasons for Patient participant Withdrawal or Discontinuation from Study Procedures/Intervention

Patient participants are free to withdraw from participation in the study at any time upon written request.

Patient participants may choose to discontinue the intervention or study procedures but continue to be followed for treatment in the practice.

The PI's study team may discontinue an individual's participation in an intervention but continue to be enrolled and provide trial data if:

- Any clinical adverse event (AE) or other medical condition or situation occurs such that continued participation in the intervention would not be in the best interest of the patient participant.
- The patient participant meets an exclusion criterion (either newly developed or not previously recognized).

The PI's study team may withdraw a patient participant from the study if:

- The patient participant fails to maintain appointments within a reasonable timeframe, i.e. If the second baseline visit has not happened within 30 days from the time of medication the patient participant is discontinued from study, and this will be considered as missing data.
- The patient participant can no longer be contacted, or patient participant has moved.

5.5.2 Handling of Patient participant Withdrawals from Study or Patient participant Discontinuation of Study Intervention

In the event that a patient participant chooses to withdraw or is withdrawn from the study, a patient participant termination form will be used to capture the date and reason for the withdrawal with no additional study data recorded. Patient participants who are withdrawn may continue to receive routine clinical care as a patient of record for the

treating dentist, but additional study data will not be collected. Data collected prior to study withdrawal will be used for the intention-to-treat analysis.

In the event that the intervention is discontinued, e.g., patient participant develops a persistent drug-related symptom such as diarrhea, prior to completing the intervention, the patient participant will continue to be enrolled in the study and the deviation from the intervention plan will be noted.

Patient participants who are withdrawn from the study after randomization will not be replaced.

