9.2 Time Period and Frequency for Event Assessment and Follow-Up

Details of UPs and AEs, including SAEs, will be recorded by the practitioner/trained office staff on eCRFs throughout the study. All events will be recorded with start dates occurring any time after informed consent is obtained until 7 (for non-serious AEs) calendar days or 30 calendar days (for SAEs) after the last day of study participation. At

each study visit, the practitioner/trained office staff will inquire about the occurrence of AE/SAEs since the last visit. If a safety event has occurred, the practitioner/trained office staff will initially complete the safety event eCRF and then contact the NC, who can assist the practitioner in completion of the eCRF. Events will be followed for outcome information until resolution or stabilization.

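### Sections 9.2 and 9.4.2 require safety recording or follow-up to continue past the end of participation, while 5.5.2, 7.6 and 15.3 stop data at withdrawal, and nothing says which governs

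*Protocol*

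**What the plan says.** Two groups of sections in the protocol address safety data around the end of participation.

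**Recording continues.** Section 9.2 has events recorded from consent "until 7 (for non-serious AEs) calendar days or 30 calendar days (for SAEs) after the last day of study participation". It adds: "Events will be followed for outcome information until resolution or stabilization". Section 9.4.2 repeats the follow-up requirement for all serious adverse events. Neither makes an exception for withdrawn participants.

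**Recording stops.** Section 5.5.2 covers both participants who choose to withdraw and those who are withdrawn. A termination form is to "capture the date and reason for the withdrawal with no additional study data recorded". Such participants may remain patients of the practice, "but additional study data will not be collected". Section 7.6, which deals with withdrawal by the participant, says: "No further information will be recorded after patient participant withdrawal request". Section 15.3 likewise ends research data collection at withdrawal.

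Three provisions bear on how large the gap is:
- Section 7.6 contains one allowance: "Record information needed to address a safety event that may have led to the" participant's withdrawal. Appendix A also marks an adverse-event assessment in its Early Withdrawal column.
- Sections 5.5.2 and 6.3 treat stopping the drug as different from leaving the study. Under 5.5.2, a participant who discontinues because of a drug-related symptom stays enrolled.
- Section 5.5.1 lists withdrawals that the study team may initiate. One of them reads: "If the second baseline visit has not happened within 30 days from the time of medication the patient participant is discontinued from study".

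**The concern.** A site cannot comply with both groups of sections. If a participant leaves with an unresolved adverse event, 9.2 tells the site to follow it and 5.5.2 and 7.6 tell it to record nothing more. If a serious event begins two weeks after withdrawal, 9.2 makes it reportable study data and 5.5.2 excludes it.

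The conflict is hardest to defend for participants withdrawn by the study team. The usual reason for closing a record is that the participant has asked for data collection to end. Someone removed because a second SRP visit was late has made no such request and has already received study product.

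At stake is a stated outcome. Section 3.2 lists the number and severity of adverse events as a safety outcome, assessed continuously through the study. Practices that resolve the contradiction differently would collect that outcome under different rules. If withdrawal rates differ between arms, so would completeness of capture.

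**Working it through.** No design figure (power, alpha or event rate) is involved, so there is no plan figure to reproduce. The check is a comparison of the sections, followed by simple day counts and an upper bound.

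**1. Days of recording after withdrawal.** The protocol does not define the last day of participation for someone who withdraws. Assume it is the withdrawal date.
- Section 9.2: 7 days for new non-serious events, 30 days for new serious events, and open-ended follow-up of events already recorded.
- Section 9.4.2: open-ended follow-up of all serious events.
- Sections 5.5.2 and 7.6: 0 days, apart from the allowance in 7.6 for an event that may have led to the withdrawal.

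**2. A participant withdrawn by the study team.** Take the case in 5.5.1 where the second baseline visit has not taken place within 30 days of medication. Put the last day of participation at day 30.
- Non-serious events under 9.2: 30 + 7 = day 37.
- Serious events under 9.2: 30 + 30 = day 60.
- Under 5.5.2: nothing after day 30.
- The drug course lasts 10 days, so the window opens about 30 − 10 = 20 days after it ends. It covers the weeks after treatment and not the dosing period.
- The re-evaluation visit is due at 6 weeks (day 42), so this participant leaves before that adverse-event inquiry.

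**3. A participant who leaves the study because of a reaction.** The triggering event is recorded under 7.6 and under the Early Withdrawal column of Appendix A. What remains in dispute is its follow-up to resolution or stabilization and any new event in the 7- or 30-day window. Section 5.5.2, read literally, does not even allow the triggering event, because its form takes only the date and the reason. So 5.5.2 also disagrees with 7.6 and Appendix A.

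**4. A participant who stops the drug but stays.** There is no conflict. Sections 5.5.2 and 6.3 provide for continued enrollment or follow-up, and 9.2 runs as written.

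**5. Which rule sites would probably follow.** Section 9.4.3 keeps a participant who becomes pregnant during the intervention in the study, without withdrawal, so that outcome and safety data can still be collected. That reasoning treats withdrawal as ending safety data, which points towards 5.5.2 and 7.6 in practice. No section states it as a rule of precedence.

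**6. Upper bound on the number affected.** Sections 5.3 and 12.2 plan for 20% attrition: 0.20 × 544 = 108.8, about 109 participants over both arms. Allocation is 1:1, so if attrition were equal by arm about half would have received active drug. The true number is below 109, because attrition also includes people who cannot be contacted, from whom no rule would recover data, and people lost late in follow-up. The protocol gives neither the timing nor the reasons.

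**The case against.** The strongest reply is that the important cases are already handled. Section 5.5.2 uses diarrhea as its own example of a reason to stop the drug, and keeps that participant enrolled. If the participant also leaves the study, 7.6 and Appendix A capture the event behind the decision. For a person who asks to leave, ending research data collection is consistent with the consent section. For a person who cannot be reached, wording makes no difference. For the late second baseline visit, the window opens well after the 10-day course.

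Most of this stands, and it rules out several stronger readings that a reader might infer:
- *Drug reactions go unrecorded when participants leave.* The triggering event is recorded. Only its later course and any new events are in doubt.
- *The safety comparison is biased towards no difference.* This would need withdrawal to differ by arm and unrecorded later events to be material. The protocol gives no basis for either, and events that prompt withdrawal still count.
- *Early leavers miss the first inquiry about adverse events after dosing starts.* Appendix A schedules assessments at the optional visit 1b and at the day-10 medication check, both before week 6. The day-10 text described in 7.3 contains no adverse-event question, but the schedule does not support the claim as stated.
- *About 109 participants exposed to active drug are affected.* The figure covers both arms and is an upper bound.

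The reply does not remove the contradiction. Section 9.2 requires recording that 5.5.2 and 7.6 forbid, consent does not explain the stop for participants whom the study team withdraws, and no section sets precedence.

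**Conclusion.** The contradiction holds in a limited form. Sections 9.2 and 9.4.2 cannot be followed together with 5.5.2, 7.6 and 15.3 for a withdrawn participant. What may be lost is the follow-up of open events and new events in the 7- or 30-day window. The clearest case is a participant withdrawn by the study team without having asked for recording to end.

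The size cannot be computed from the protocol. It is at most about 109 of 544 participants under the planned attrition, and realistically fewer. The day counts rest on taking the withdrawal date as the last day of participation, which the protocol leaves undefined. The consequence is confined to completeness of the adverse-event outcome. The probing-depth analysis and the sample size do not depend on it. The correction is inexpensive and should be made, because it decides which safety events enter a stated outcome.

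**What to change.** Reconcile 5.5.2, 7.6, 9.2, 9.4.2 and 15.3 in one amendment:

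1. Define the last day of participation for withdrawn participants.
2. Separate withdrawal of consent to any further data from withdrawal by the study team or from study procedures only. For the latter, state that the 9.2 windows and the follow-up of open events continue.
3. For participants who ask to leave, record on the termination form whether safety follow-up may continue.
4. Bring 5.5.2 into line with the safety-event item in 7.6 and the Early Withdrawal assessment in Appendix A, so that the termination procedure is not limited to date and reason.

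A dedicated safety call at the end of the 30-day window would be one way to carry this out, but no section requires it and the correction does not depend on it.

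The cost is amendment wording and one added field on the termination form. The downside is slightly more contact with people who have left, subject to their consent.
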